###### Treatment

- After signing the consent form, the participant will complete a paper form collecting contact information for follow-up and demographic information. At this point, the participant will be assigned a participant ID number. The researcher will verify the participant's diagnostic code and therapist using AHLTA afterward.
- Before the participant's next PT appointment, the participant will complete the baseline questionnaire battery, a 139 question survey battery. The participant may complete the battery immediately on paper, or at a later date online using a link to REDCap that will be sent via encrypted email. This battery must be completed before their next appointment.
- Participants will receive standard PT care as prescribed and scheduled by their therapist. Participation in the study will not alter their care plan.
- Participants will complete follow up questionnaire batteries after their 4th PT appointment\*, 6mo and 12mo post enrollment. The first follow-up questionnaire is a 77 question survey battery. The second and third follow-up points use a 68 question battery. All follow-up questionnaires will be completed remotely via REDCap.
- We will collect de-identified SOAP notes from randomly selected participants and review them for verbiage indicating that the therapist employed principles of PiPT. We will collect up to 30 SOAP notes, pertaining to various physical therapists and throughout various stages of treatment.

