### Treatment

- After signing the consent form, the participant will complete a paper form collecting contact information for follow-up and demographic information. At this point, the participant will be assigned a participant ID number. The researcher will verify the participant's diagnostic code and therapist using AHLTA afterward.
- Before the participant's next PT appointment, the participant will complete the baseline questionnaire battery, a 139 question survey battery. The participant may complete the battery immediately on paper, or at a later date online using a link to REDCap that will be sent via encrypted email. This battery must be completed before their next appointment.
- Participants will receive PT care as prescribed and scheduled by their therapist. Participation in the study will not directly alter their care plan.
  - During Phase II, we anticipate that therapists who completed PiPT training will incorporate the training into their standard care. We will not ask therapists to give differential treatment to patients who are enrolled in the study.
- Participants will complete follow up questionnaire battery after their 4th PT appointment, 6mo and 12mo post enrollment. The first follow-up questionnaire is a 77 question survey battery. The second and third follow-up points use a 68 question battery. All follow-up questionnaires will be completed remotely via REDCap.
- We will collect de-identified SOAP notes from randomly selected participants and review them for verbiage indicating that the therapist employed principles of PiPT. We will collect up to 30 SOAP notes, pertaining to various physical therapists and throughout various stages of treatment.

We chose to conduct this study in sequential cohorts rather than conducting the two cohorts (PiPT and non-PiPT) in parallel because there are no comparable sites with similar characteristics such as type of subjects, catchment area size and availability of the health care team in the Navy.

\*We chose the 4th visit as the first follow-up point for two reasons. First, we expect to see a difference between groups on study outcomes at that point. Secondly, since according to the former head of the NMCP department of physical therapy (PI) the average number of visits at the outpatient PT clinic is 6, the 4th visit will allow us to capture complete data.

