#### Intake Form (Demographics)

C  
o  
II  
V  
A  
R  
T  
I  
O  
A  
n  
B  
L  
P  
L  
E  
i  
n  
t

I D F  
n Si e r  
Gt n me  
e a glo e n  
n k e g R /  
d e It r e a  
e F e a s  
r o m p p  
r hio  
m c n  
s s  
e  
F  
I D r  
n e e  
t Sim e  
a n o e  
A k glg R n  
g e r e /  
e It a s a  
F e p p  
o mhi o  
r c n  
m s s  
e

F  
MI D r  
a n e e  
a n Sim e  
rit n o e  
t a glg R n  
alk e r e /  
ste It a s a  
a F e p p  
t o mhi o  
u r c n  
s m s s  
e

I D  
I e  
n Sim Y  
t a n o e  
h k glg s n  
n i e r e /  
c i It a N a  
t F e p N  
y o mhi o  
r c  
m s

I D  
I e S  
n Simel  
t n o e  
Ra glg ctn  
a k e r fr /  
c e It a o a  
e F e p m  
o mhi Li  
r c st  
m s

L  
e  
n I D F  
g I e r  
t t Sim e  
h t n o e  
of a glg R n  
s k e r e /  
e It a s a  
r F e p p  
m n

vio his  
c r c e  
e m s  
F  
R I D r  
R n e e  
a t Sime  
t t n o e  
e k glg n  
/ e r s /  
R Ita a  
a F e p p  
a o e p o  
n mhi o  
k r c n  
k m s s  
e e  
D  
E D a  
v I Da  
e t  
aln Sime  
u t n o ( a a  
a a glg d n  
tik e r d /  
o e Ita Ma  
n F e p O  
Do mhi N  
a r m  
t m c y  
e s y  
)  
T I D L  
h n e L  
e t m a  
r A o s t  
a a H g n n  
a k L r a n  
pi e T a m a  
st F a p e  
N o A p e,  
a r h i F i  
m r h i r s  
m m c t  
e s  
I D I  
n e C  
D t m D  
ia A o -  
g a H g n  
n k L r 1 /  
o e T a o  
si F A p C  
s o A p o  
s r h i d  
m c e  
s

**Evaluation Date:** Because participants will be consented and fill out the intake form on the day of their PT evaluation, the research staff member will simply record the current date that the form is completed.

We will require a DSA to harvest those last two variables.

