### 13.0

#### Recruitment and Consent

##### 13.1 Please describe the recruitment process, including how subjects will be identified and selected for the study.

Research staff will approach pre-screened patients immediately after their evaluation appointment with their physical therapist, inform them of the study, and ask them if they are interested in participating. Interested patients will then be lead to a private study area nearby to begin the consenting process described in Section 13.4. Those who consent will leave us their contact information and may complete their baseline questionnaire immediately on location, or they may complete it remotely before their next appointment.

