#### **14.5 Privacy for Subjects:**

Describe the measures to protect subject's privacy during recruitment, the consent process, and all research activities, etc.

Recruiting and consenting: We intend to rely on physical therapy staff to introduce us to eligible patients in their exam room after their evaluation session, so that participants can be briefed on the study in private. Interested patients will be provided a private space in the PT clinic to review the consent form and ask questions.

Participation: Participants may either complete their baseline questionnaire in person or online; all follow-up questionnaires will be completed remotely. If they choose to participate in person, they will complete the questionnaire in paper in the consenting area. The online method will consist of the research team sending a link to the online questionnaire via encrypted email to the address specified by the participant. The online questionnaire will be hosted on REDCap.

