## 16.0 Reportable Events

### 16.1 Reportable Events: Consult with the research office at your institution to ensure requirements are met. Describe plans for reporting unexpected adverse events and unanticipated problems. Address how unexpected adverse events will be identified, who will report, how often adverse events and unanticipated problems will be reviewed to determine if any changes to the protocol or consent form are needed and the scale that will be used to grade the severity of the adverse event.

Consult with the research office at your institution to ensure requirements are met

- Describe plans for reporting expected adverse events. Identify what the expected adverse events will be for this study, describe the likelihood (frequency, severity, reversibility, short-term management and any long-term implications of each expected event)
- Describe plans for reporting unexpected adverse events and unanticipated problems. Address how unexpected adverse events will be identified, who will report, how often adverse events and unanticipated problems will be reviewed to determine if any changes to the research protocol or consent form are needed and the scale that will be used to grade the severity of the adverse event

We believe that the most likely adverse events are already described under "Incidental Findings" (Section 14.6). Beyond those, the most plausible adverse events we foresee are possible breaches of privacy and/or confidentiality and the potential distress of answering questions regarding mental health, which are also previously explored in Section 14.1.

Any reportable events, expected or not, will result in our team submitting a Note to File to the IRB within 24 hours of discovery. Serious adverse events and unanticipated problems will be reported to the Research Subject Protection Division within 24 hours. Similarly, any protocol violations will be reported within five business days. Other events such as non-serious adverse events and protocol deviations will be reported with the next continuing review unless they require a protocol modification. In that instance, the event will be reported alongside the modification.

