Research staff will inquire whether any adverse events (AEs) have occurred at each in-person encounter with participants, and REDCap surveys will include instructions for contacting the research coordinator or PI if an AE has occurred. All research staff interacting with participants will maintain blank AE Log forms. Due to the large sample size and low risk, an AE Log will not be maintained for every participant, only those involved in an AE.

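### Adverse events are actively asked about only in person, but all three follow-ups are remote, so no active inquiry is planned after the enrolment day

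*Combined protocol and SAP*

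**What the plan says.** Section 16.1 sets out two routes for learning of adverse events. The active one is in person: "Research staff will inquire whether any adverse events (AEs) have occurred at each in-person encounter with participants". The passive one is for remote contact: "REDCap surveys will include instructions for contacting the research coordinator or PI if an AE has occurred". A log is opened only for participants who have an event.

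The mode of follow-up is stated in three places. The Treatment parts of Section 10.1, for both Phase I and Phase II, say "All follow-up questionnaires will be completed remotely via REDCap". Section 14.5 agrees: "Participants may either complete their baseline questionnaire in person or online; all follow-up questionnaires will be completed remotely".

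In-person research contact is described only around the evaluation appointment. Section 10.2 explains how the evaluation date is recorded: "Because participants will be consented and fill out the intake form on the day of their PT evaluation". Section 13.1 adds that those who consent "may complete their baseline questionnaire immediately on location, or they may complete it remotely before their next appointment".

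Among plausible events, Section 16.1 lists "the potential distress of answering questions regarding mental health". Section 14.1 ties that risk mainly to the initial questionnaire, with its depression, anxiety and PTSD measures. Section 14.6 provides a referral step when baseline scores on the PCL-M, CES-D or GAD-7 exceed stated thresholds.

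**The concern.** A rule that ties the question to in-person contact works only if in-person contact continues. Here it stops on the first day, while participation runs for 12 months. The written commitment to ask therefore has no planned occasion on which to operate during follow-up.

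The responses to distress in Sections 14.1 and 14.2 depend on someone noticing that a participant is upset. Nobody is present when a survey is completed at home. The 24-hour reporting clock in Section 16.1 starts at discovery, so it gives no protection against an event that is never discovered. Because logs exist only for participants with an event, the record would also not show who was asked and had nothing to report, as distinct from who was never asked. A low count at the end of the study would then be hard to interpret, although confirming low risk is what such a record is for.

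**Working it through.** No power or sample-size formula applies. The check sets the provisions side by side and then tests whether an adverse event question could already sit inside the follow-up batteries.

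**Step 1: planned contacts and the type of inquiry at each**

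| Contact | Mode | Source | Adverse event inquiry |
|---|---|---|---|
| Enrolment day: briefing, consent, intake form, optional paper baseline | In person | Sections 10.1, 10.2, 13.1 | Active |
| Baseline battery, if done later | Online | Sections 10.1, 13.1, 14.5 | Contact instructions only |
| After the fourth visit | Online | Sections 10.1, 14.5 | Contact instructions only |
| 6 months | Online | Sections 10.1, 14.5 | Contact instructions only |
| 12 months | Online | Sections 10.1, 14.5 | Contact instructions only |

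No later telephone call, research visit or chart check for adverse events is described. Section 10.14 uses CHCS and AHLTA to find the date of the fourth session, for scheduling only. Participants do return to the clinic for therapy, but Section 16.1 gives the inquiry to research staff, and nothing assigns it to the treating therapist.

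Planned active inquiries after the enrolment day are therefore 0 of 3 per participant. With the 600 participants of Section 11.2, that is at most 600 × 3 = 1,800 follow-up surveys without a direct question. The number actually completed would be lower because of attrition.

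**Step 2: is there an adverse event item in the follow-up surveys?**

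Section 10.2 states 77 items at the first follow-up and 68 at 6 and 12 months. The item counts in its follow-up table are:

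- single items: injury location 1, pain intensity 1, outcome expectation 1, quality of life 1, outcome satisfaction 1, duty status 1, lessons learned 1 (sum 7)
- PDI 7, PSEQ 10, PCS 13, FABQ 15, HADS 14 (sum 59)
- mental health care 3, MRPS process of care 8 (sum 11)

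Total: 7 + 59 + 11 = 77, which reproduces the stated figure. Removing the MRPS (8) and outcome expectation (1) gives 77 − 8 − 1 = 68, which also matches. No item is left over that could be an adverse event question. The table is badly broken in the extracted text, so the individual counts needed some reading, but both totals reconcile exactly.

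**Step 3: which sensitive instruments fall where?**

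The PCL-M, CES-D and GAD-7 appear in the baseline table and not in the follow-up table. Two groups follow:

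- *Paper baseline on site.* Research staff are still present during and after the battery, so the in-person inquiry can cover it.
- *Online baseline.* The participant has left before answering, so the only active inquiry precedes these questions.

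The protocol does not say what share will choose each mode.

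The HADS is repeated at all three follow-ups. Section 14.6 limits its score-triggered step to baseline and to the three instruments above. At follow-up the plan therefore has neither an active question nor a stated score trigger.

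**The case against.** The best defence is that the plan does address remote contact. The sentence that limits active inquiry to in-person encounters goes on to provide contact instructions in the surveys. The instruments the protocol singles out for distress are given only at baseline, and they can be completed on paper with a researcher present. Other safeguards exist: the baseline score thresholds in Section 14.6, a clinical psychologist as research monitor, and a team psychologist who may act on distress data under Section 14.3. Section 16.1 regards incidental findings as the most likely events, and those come from scores and SOAP notes rather than from asking participants. The study is observational and does not direct individual care.

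Much of this stands, and it limits the weight of the point. It does not close the gap, because contact instructions depend on the participant taking the initiative. Section 14.3 gives no threshold or timing for looking at follow-up scores.

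Four stronger readings are tempting, and the documents do not support them:

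- *That events after enrolment cannot be captured.* They can, by the passive route or at an unscheduled meeting.
- *That everyone is asked before completing any survey.* This is so only for those who do the baseline online.
- *That the cohorts could not be compared on adverse events.* No aim or analysis makes that comparison, and the collection procedure is the same in both phases.
- *That some given fraction of events would be missed.* The documents contain neither an event rate nor a capture rate, and any percentage would only restate an assumption.

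**Conclusion.** The point holds for active inquiry. As written, nobody is asked about adverse events after the enrolment day: 0 of 3 follow-ups, for up to 600 participants over 12 months. Those who complete the baseline online are not asked after the depression, anxiety and PTSD questions either. Later detection rests mainly on participants contacting the team themselves.

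This rests on two readings: that the in-person contacts described in the protocol are the only ones planned, and that the follow-up table lists every item. The exact match to 77 and 68 supports the second. The number of events that would go unreported cannot be estimated from the documents.

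The change is worth making because it is cheap and covers a period in which the plan has only a passive route. It is a modest improvement to safety monitoring in a low-risk study, and no efficacy result is affected.

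**What to change.** Add one yes/no item to every REDCap survey, meaning the online baseline and all three follow-ups. It should ask whether the participant has had any problem or distress that they think is related to the study, with a free-text box that opens on a yes. At follow-up the reference period is since the last survey. At baseline the item should come at the end, after the mental health instruments. For paper baselines, staff can record the answer to the in-person question in the same field.

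Set an automatic alert so that a yes reaches the research coordinator, who handles it through the existing Section 16.1 pathway. Amend Section 16.1 to say that inquiry is made in person and in each survey, and keep the contact instructions. Update the item counts in Sections 10.1 and 10.2: counting the free text as part of the item, 77 becomes 78, 68 becomes 69, and the baseline count of 139 becomes 140.

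The cost is one extra item per survey, an IRB modification and a few more non-serious reports to log. No new visits or staff are needed. The item changes no treatment or referral rule; whether follow-up scores should have a trigger of their own is a clinical question outside this point.

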## 17.0 Equipment/non-FDA Regulated Devices

### 17.1 Does the study involve the use of any unique non-medical devices/equipment?

Yes  No

## 18.0 FDA-Regulated Products

### 18.1 Will any drugs, dietary supplements, biologics, or devices be utilized in this study?

- Drugs
- Dietary Supplements
- Biologics
- Devices
- N/A

### 18.5 Sponsor (organization/institution/company):

N/A

If applicable, provide sponsor contact information:

## 19.0 Research Registration Requirements

### 19.1 ClinicalTrials.gov Registration:

- Registration is not required
- Registration pending
- Registration complete

### 19.2 Defense Technical Information Center Registration (Optional):

- Registration is not required
- Registration pending
- Registration complete

## 20.2 Abbreviations and Acronyms:

**ADSM – Active Duty Service Members**

**AHLTA – Armed forces Health Longitudinal Technology Application**

**CBT – Cognitive Behavioral Therapy.**

**CES-D – Center for Epidemiologic Studies Depression Scale**

**CID – Clinical Investigations Department at NMCP**

**COMI – Core Outcome Measures Index**

**CDMRP – Congressionally Directed Medical Research Programs**

**CRADA – Cooperative Research and Development Agreement**

**DRRI – Deployment Risk and Resilience Inventory-2**

**FAB – Fear avoidance beliefs**

**FABQ – Fear Avoidance Beliefs Questionnaire**

**GAD-7 – General Anxiety Disorder Screener**

**HADS – Hospital Anxiety and Depression Scale**

**ICD – International Classification of Diseases**

**IFC – Informed Consent Form**

**IRB – Institutional Review Board**

**LBP – Low Back Pain**

**MRPS – MedRisk Instrument for Measuring Patient Satisfaction**

**MSD – Musculoskeletal Disorders**

**NMCP – Navy Medical Center Portsmouth**

**NYU – New York University**

**PCL-M – PTSD Checklist Military Version**

**PCS – Pain Catastrophizing Scale**

**PDI – Pain Disability Index**

**PEB – Physical Evaluation Board**

**PHI – Personal Health Information**

**PI – Principle Investigator**

**PiPT – Psychologically-informed Physical Therapy**

**PSEQ – Pain Self-efficacy Questionnaire**

**PT – Physical Therapy**

**PTSD – Post-traumatic Stress Disorder**

**RA – Research Assistant**

**RCT – Randomized Controlled Trial**

**SOAP note – Subjective, Objective, Assessment, and Plan note**
